9.5.3 Clinical and Laboratory Assessments

Clinical and laboratory assessments include clinical laboratory tests (hematology, coagulation, urinalysis, thyroid function tests and chemistry), vital signs, ECHO and 12-lead ECGs.

Clinical laboratory results will be listed by patient and, as appropriate, summarized descriptively, which will include a display of change from baseline. Selected parameters will be presented in shift tables of baseline against worst grade test result. Laboratory values outside of the normal ranges will be identified. Laboratory values that meet Grade 3 or 4 criteria according to NCI CTCAE v.4.03 will be listed and summarized.

ECG assessments will be evaluated for change of QTc from baseline as an exposure: response analysis. The Investigator's interpretation of QTc will be used in the clinical management of patients. The study analysis will use Fridericia's formula applied programmatically to the ECG data collected in CRFs.

Vital signs, ECHO and ECG measurements will be listed for each patient at each visit. Descriptive statistics of observed values and changes from baseline will be summarized by treatment group.

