8.4 Safety Variables

With regard to safety summaries, the term “on-treatment” is the period from first dose until either last dose + 28 days or the start of anti-cancer therapy, whichever is earlier.

AEs, laboratory values and ECGs will be graded according to the NCI CTCAE v4.03 (see Section 13.0 for link to the criteria), ECGs will also be graded according to International Conference on Harmonisation (ICH) E14.

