11.1.7.4 Laboratory Data

Laboratory data will be presented for hematology, chemistry, urinalysis and thyroid function tests (see Table 6 for a list of specific parameters under each category), by scheduled visit using the Safety Population for patients with at least 1 measurement for each parameter, regardless of whether or not a baseline assessment is present. Unscheduled visits will be included in any presentation of minimum, maximum or worst case summaries across all cycles.

All laboratory data will be summarized in International System (SI) units, with selected chemistry parameters repeated using British imperial units commonly used in the United States. The conversion factors from conventional units to SI units are documented in the Lab Loader Specification (v1.0 October 13th 2020) for this study.

Descriptive statistics will be provided for each parameter result and associated changes from baseline by cycle. Multiple measurements taken during a given visit for a patient will be represented by the most severe value for each parameter. Criteria for selecting the most severe value in these cases are described in the category specific sections below.

Shift tables for selected parameters will present shifts in CTCAE grades from baseline to each post-baseline scheduled visit, to the maximum post-baseline grade (including unscheduled visits), and to the last assessment.

All clinical laboratory results will be listed, with any laboratory values meeting NCI CTCAE Grade 3 or 4 criteria being listed separately.

CTCAE Coding of Laboratory Data

Grades are applied based only on the numeric SI value of the parameter assessed; clinical signs and symptoms are not considered. For example, Grade 4 hyperglycemia will be assigned based solely on the value of the glucose measurement, and acidosis will not be considered. Where categories are only distinguished by clinical signs or symptoms, the lowest of the possible grades will be assigned.

NCI CTCAE grades will be applied for the following lab parameters:

- Hematology: hemoglobin, WBC, lymphocyte, neutrophils, and platelets.
- Chemistry: ALT, albumin, alkaline phosphatase, AST, total bilirubin, calcium, creatinine, magnesium, potassium, sodium, uric acid.

Laboratory measurements that are within their institutional limits of normal and are not graded as 1-4, per the CTCAE, will be summarized as "Grade 0," which is defined as normal.

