11.1.7.4.2 Chemistry

Selected chemistry parameters will be repeated using British imperial units commonly used in the US, refer to Section 8.4.6 and the notation ^{IU} within Table 6.

If a patient has multiple measurements taken during the visit for a patient will be represented by the most severe value for each chemistry parameter. The most severe value will be determined using the following criteria;

High values are considered the most severe for all chemistry parameters, unless otherwise noted in Section 8.4.6 and the notation ^{Low or High or Low} within Table 6. The most severe value will be determined using the same criteria described for Hematology parameters,

Shift tables will present shifts in CTCAE grades from baseline for the following selected chemistry parameters;

- AST (AST Increased),
- ALT (ALT Increased),
- Creatinine (Creatinine Increased),
- Sodium (both Hyponatremia and Hypernatremia),
- Potassium (both Hypokalemia and Hyperkalemia),
- Phosphate (Hypophosphatemia),
- Uric Acid (Hyperuricemia).

For parameters where separate grading criteria exists, all low values will be included in the Grade 0 group when summarizing high values as being most severe and vice versa (all high values will be included in the Grade 0 group when summarizing low values as being most severe).

Patients who develop a Grade ≥ 3 toxicity will be also listed separately.

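### The SAP's list of CTCAE-graded laboratory tests disagrees with the text around it, and the SAP plans no dedicated Grade 3-4 summary although Protocol 9.5.3 says there will be one

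*SAP*

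**What the plan says.** **Grading scope.** SAP 8.4 sets the general rule: "AEs, laboratory values and ECGs will be graded according to the NCI CTCAE v4.03". SAP 11.1.7.4 then narrows it. Under its coding subsection, "NCI CTCAE grades will be applied for the following lab parameters", followed by five hematology tests and this chemistry list: "Chemistry: ALT, albumin, alkaline phosphatase, AST, total bilirubin, calcium, creatinine, magnesium, potassium, sodium, uric acid". Just before that list, to show that grading ignores clinical signs, the same subsection states that "Grade 4 hyperglycemia will be assigned based solely on the value of the glucose measurement".

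**Grade 3-4 output.** Protocol 9.5.3 names two outputs. One is selective: "Selected parameters will be presented in shift tables of baseline against worst grade test result". The other is not: "Laboratory values that meet Grade 3 or 4 criteria according to NCI CTCAE v.4.03 will be listed and summarized". SAP 11.1.7.4 provides for all results to be listed, "with any laboratory values meeting NCI CTCAE Grade 3 or 4 criteria being listed separately". SAP 11.1.7.4.1 and 11.1.7.4.2 add that patients reaching Grade 3 or above are listed separately. The SAP also plans shift tables for selected tests, including shifts to the maximum post-baseline grade with unscheduled visits counted.

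**Phosphate.** SAP 11.1.7.4.2 includes a hypophosphatemia shift table. Phosphate is not in SAP Table 6, the graded list or Protocol Table 19.

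**The concern.** The passages do not give a programmer one consistent specification. For glucose, the example and the list point in opposite directions within one subsection. For lipase and amylase, the closed list leaves out two collected tests whose grades the protocol itself uses: the footnote to Protocol Table 15 has a category for Grade 3 amylase or lipase elevation. If the list is followed, Grade 3-4 values of these three tests drop out of the Grade 3-4 listings.

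The missing summary is a separate matter. The incidence and severity of laboratory abnormalities are part of a named secondary endpoint (Protocol 2.2.2, SAP 5.2.2). A listing gives no incidence. Where a graded test has no shift table, the safety report would contain no count of patients with a Grade 3 or 4 value, although the protocol says such values will be summarized.

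**Working it through.** The plan gives no figure to reproduce. The check compares lists of tests.

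**Inputs**

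- Graded list, SAP 11.1.7.4: hematology 5 (hemoglobin, WBC, lymphocytes, neutrophils, platelets) and chemistry 11, together 5 + 11 = 16.
- SAP Table 6: hematology panel 7 (including INR and PTT) and chemistry panel 19, together 26.
- Shift tables: hematology 4 (hemoglobin, neutrophils, platelets, lymphocytes; SAP 11.1.7.4.1) and chemistry 7 (AST, ALT, creatinine, sodium, potassium, phosphate, uric acid; SAP 11.1.7.4.2), together 11.
- Collected tests: Protocol Table 19.

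**Step 1: panel against graded list.** All 16 graded tests are in Table 6, so 26 − 16 = 10 panel tests are off the list: INR, PTT, direct and indirect bilirubin, BUN, chloride, bicarbonate, glucose, lipase and amylase. The documents treat the tests in question as follows:

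| Test | Collected (Protocol Table 19, SAP Table 6) | On graded list | Text elsewhere that points to a grade |
|---|---|---|---|
| Glucose | yes, non-fasted | no | worked example in the same subsection |
| Lipase, amylase | yes | no | general statements only (SAP 8.4 and the Grade 3-4 listing sentence); Grade 3 category in the Protocol Table 15 footnote |
| Phosphate | no | no | shift table by CTCAE grade in SAP 11.1.7.4.2 |

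**Step 2: graded list against shift tables.** Graded tests with a shift table: hematology 4 + chemistry 6 (the seven chemistry entries less phosphate) = 10. Graded tests without one: 16 − 10 = 6, namely WBC, albumin, alkaline phosphatase, total bilirubin, calcium and magnesium. Share: 6/16 = 37.5%. For these six, the only named output by grade is a listing.

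**Step 3: phosphate.** One of the seven chemistry shift-table entries has neither a planned data source nor a place on the graded list.

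**Step 4: was the change declared?** SAP 4.1.1 to 4.1.5 cover glesatinib, mocetinostat, analysis populations, clinical benefit rate and the PK sub-studies. None concerns laboratory output.

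**Step 5: would the adverse event tables supply the count?** Only in part. Protocol 8.2.1 makes an abnormal value an adverse event only if it meets at least one condition: symptoms, further tests or treatment, a dosing change, discontinuation, or a judgement by the investigator or sponsor. Protocol 5.1.4.2.5 allows sitravatinib to continue unmodified for asymptomatic amylase or lipase increases without other evidence of pancreatitis. Such a rise need not meet any of the conditions and may then exist only as a laboratory value.

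For context, Protocol Table 5 reports treatment-related Grade ≥3 events on sitravatinib monotherapy of lipase 6/153 = 3.9%, amylase 2/153 = 1.3% and hypophosphatemia 5/153 = 3.3%. These were reported as adverse events in another study and do not estimate what would be missed here.

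**The case against.** The case on the other side has weight, and several stronger readings fall to it.

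- **A reader might infer that the SAP plans no Grade 3-4 laboratory summary at all.** It does not go that far. Shift tables to the maximum post-baseline grade give Grade 3 and 4 counts for 10 of the 16 graded tests, and Protocol 9.5.3 leaves the choice of shift-table tests to the sponsor. What is missing is the dedicated summary, and its absence bites on six graded tests. SAP 11.1.7.4 alludes to worst-case summaries across cycles but names no such table by grade.
- **A reader might infer that the SAP contradicts itself on lipase and amylase as it does on glucose.** No SAP sentence says that either is graded. SAP 8.4 can be read as naming the CTCAE version, with Section 11 setting the scope: it speaks of ECGs just as broadly, yet SAP 11.1.7.6 grades only QTcF. For these two tests the fault is omission from a closed list, in tension with general statements. Only glucose meets a direct conflict.
- **A reader might add the three tests to the six and quote a combined share.** The denominator would be arbitrary, because seven other Table 6 tests are also off the list.
- **A reader might infer that there are no phosphate data.** SAP 8.4.6 describes Table 6 as routine tests, and Protocol 7.2.3 allows others. Absence from the panels does not prove absence from the database.
- **The sponsor may change plans in the SAP.** Protocol 9 permits this. Declaring the omission in SAP 4.1, and replacing the glucose example, would settle the paperwork. It would not supply the count.

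Also on this side: all results are listed, chemistry and hematology are described by cycle, reported adverse events are tabulated by maximum grade, and bilirubin appears against ULN in the eDISH figures.

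**Conclusion.** The point holds as a minor inconsistency in the safety specification. Glucose is in direct conflict within SAP 11.1.7.4. Lipase and amylase are left off the graded list despite being collected and despite the protocol's own use of their grades. The summary in Protocol 9.5.3 has no dedicated counterpart in the SAP and no declared change, which leaves 6 of 16 graded tests (37.5%) without a grade-based count. Phosphate has a shift table with no planned source.

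This rests on two readings: that the list introduced in 11.1.7.4 is exhaustive, as its wording suggests, and that Protocol 9.5.3 means the Grade 3-4 summary to be separate from the shift tables, since it gives each its own sentence. The documents do not say how many Grade 3-4 values would go unreported as adverse events, so the practical loss cannot be sized. No efficacy result, Type 1 error figure or expansion rule is affected.

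**What to change.** 1. In SAP 11.1.7.4, add glucose, lipase and amylase to the graded list so that it agrees with the example and the general statements. Footnote that glucose samples are non-fasted.
2. Add one table for the Safety Population: for each graded hematology and chemistry test, the number and percentage of patients with any post-baseline Grade 3 or 4 value, unscheduled visits included. This delivers what Protocol 9.5.3 describes. Further shift tables are optional.
3. Check the database for phosphate. If values exist, add phosphate to Table 6 and the graded list; if not, delete its shift table.

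The cost is one extra table and a few lines of text. Glucose, lipase and amylase are already collected, and SAP 4.0 provides for a final version before database lock.

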**Table 6:**

Hematology Panel	Chemistry Panel

 • Hemoglobin ^{High or Low} • Platelet Count • White Blood Cell (WBC) Count • Neutrophil Count • Lymphocyte Count ^{High or Low} • International Normalized Ratio (INR) • Partial Thromboplastin Time (PTT) 	
 • Alkaline Phosphatase • ALT • AST • Total Bilirubin ^{IU} • Direct Bilirubin ^{IU} • Indirect Bilirubin ^{IU} • Lipase • Amylase • Creatinine ^{IU} • Blood Urea Nitrogen (BUN) ^{IU} • Chloride ^{Low} • Bicarbonate [CO₂] ^{Low} • Sodium ^{High or Low} • Potassium ^{High or Low} • Glucose (Non-Fasted) ^{High or Low} • Albumin ^{Low} • Calcium ^{High or Low / IU} • Magnesium • Uric Acid
Urinalysis (Dip Stick)	

 • Blood • Protein 	
Thyroid Function Test	

 • Thyroid Stimulating Hormone (TSH) • Free-T4 	

IU: Indicates Chemistry parameter that will be summarized twice, once in SI units and once in Imperial units.

Low: Indicates Chemistry parameter where most severe values are low.

High or Low: Indicates parameter where most severe values can be in either direction.

11.1.7.4.1 Hematology

If a patient has multiple measurements taken during a given visit the most severe value for each hematology parameter. The most severe value will be determined using the following criteria;

Severity in One Direction (Either Low or High);

- If the values are all within the normal range, select the value closest to the upper or lower limit of the normal (dependent on which direction is considered severe)
- If at least one value is outside of the normal range, select the value furthest from the upper or lower limit will be selected (dependent on which direction is considered severe).
- In the event that this algorithm does not allow for determining the most severe (e.g. a tie), select the first chronological value.

Severity in Both Directions (Both Low and High);

- If the values are all within the normal range, select the value closest to the normal limit (in either direction)
- If at least one value is outside the normal range, select the value most distant from the normal limit (in either direction)

In the event that this algorithm does not allow for determining the most severe (e.g. a tie), select the first chronological value.

Low values are considered the most severe for all hematology parameters, unless otherwise noted in Section 8.4.6 and the notation ^{High or Low} within Table 6.

Shift tables will present shifts in CTCAE grades from baseline for the following hematology parameters;

- Hemoglobin (Anemia and Hemoglobin Increased),
- Neutrophils (Neutrophil Count Decreased),
- Platelets (Platelet Count Decreased)
- Lymphocyte Count (Lymphocyte Count Decreased and Lymphocyte Count Increased)

Patients who develop a \geq Grade 3 toxicity will be also listed separately.

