8.4.6 Clinical Laboratory Assessments

Clinical laboratory parameters to be collected routinely for hematology, chemistry, urinalysis and thyroid function are listed in Table 6 in Section 11.1.7.4 .

Pregnancy Testing: For patients of childbearing potential, a serum or urine pregnancy test will be performed by the local laboratory at screening. Pregnancy tests will also be done whenever pregnancy is suspected during the study.

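### The SAP's default makes low INR and PTT the most severe values, and its planned hypophosphatemia shift table has no matching laboratory parameter

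*SAP*

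**What the plan says.** SAP 11.1.7.4 sets the rule for repeats: "Multiple measurements taken during a given visit for a patient will be represented by the most severe value for each parameter". The direction of severity comes from the sections that follow.

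- **Hematology (11.1.7.4.1).** "Low values are considered the most severe for all hematology parameters, unless otherwise noted in Section 8.4.6"; the only other exception is the High or Low notation in Table 6. In the Hematology Panel, hemoglobin and lymphocyte count carry that notation. INR and PTT sit in the same panel with no mark.
- **Section 8.4.6.** It contains no exception on direction and refers back to the table: "Clinical laboratory parameters to be collected routinely for hematology, chemistry, urinalysis and thyroid function are listed in Table 6". Coagulation is not named as a category. Protocol Table 19 and protocol 9.5.3 do treat it as a separate one.
- **Table 6 legend.** It defines a units mark, a Low mark ("Indicates Chemistry parameter where most severe values are low") and a High or Low mark. There is no High mark.
- **Selection rule (11.1.7.4.1).** If all repeats are normal, the value nearest the limit on the severe side is taken. If any is out of range, the text says "select the value furthest from the upper or lower limit will be selected", with a parenthesis tying the choice of limit to the severe direction.
- **Chemistry (11.1.7.4.2).** High is the default direction. Shift tables are planned for seven parameters, one of them phosphate, for hypophosphatemia.

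**The concern.** For a clotting test the value of safety interest is the prolonged one. Protocol 5.1.2.4.4 calls the hemorrhagic risk with sitravatinib unknown and notes such events with VEGFR inhibitors. A rule labelled most severe that points to the low side of INR and PTT therefore works against its own purpose. The likely cause is that a separate protocol panel was moved into a panel with a Low default.

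The phosphate item is a different kind of fault: an output is specified for a parameter that neither document lists as collected or graded. The analyte matters here. Protocol Table 5 reports treatment-related hypophosphatemia on sitravatinib monotherapy in 9 of 153 patients (6%), 5 of them at Grade 3 or higher (3%).

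At stake are by-visit INR and PTT summaries that show the less concerning repeat, and one safety table that cannot be programmed from the plan.

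**Working it through.** The plan gives no figure to reproduce. The check applies its rule to pairs of values and compares its lists. The normal ranges below are assumptions; the documents give none.

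**1. Direction for INR and PTT.** Hematology Panel, no mark, no exception in 8.4.6, no High mark available: the Low default applies.

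**2. All repeats normal.** Let a < b both lie between limits L and U. With low severe, the rule takes the value with the smaller distance to L. Since a − L < b − L, it takes a. This holds for any range.
- INR, range 0.9–1.2, values 0.95 and 1.15: distances 0.05 and 0.25, so 0.95 is reported.
- PTT, range 25–35 s, values 28 and 34: distances 3 and 9, so 28 is reported.

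**3. One repeat prolonged.** The wording allows two readings: (A) take the lowest value; (B) take the largest absolute distance from the lower limit.
- INR 1.1 and 3.5: A gives 1.1. B compares 0.2 with 2.6 and gives 3.5.
- PTT 30 and 70: A gives 30. B compares 5 with 45 and gives 70.

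So a prolonged value is passed over under A and kept under B.

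**4. What B would do elsewhere.** Platelets, lower limit 150, values 100 and 300: A gives 100. B compares 50 with 150 and gives 300, a normal value. The two-directional bullet has the same gap: sodium, range 135–145, values 134 and 140, distances 1 and 5, so literal distance gives 140.

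**5. Phosphate.** Shift tables: 4 hematology + 7 chemistry = 11 parameters. Ten appear in both Table 6 and the graded list. Phosphate appears in neither, nor in protocol Table 19.

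**6. Safeguards.** Table 6 has 7 hematology + 19 chemistry = 26 parameters in these two panels. The graded list names 5 + 11 = 16, all of them in Table 6; INR and PTT are not among them. Shift tables run to each scheduled visit, "to the maximum post-baseline grade (including unscheduled visits), and to the last assessment", but exist for only 10 of the 16. The other 16 − 10 = 6 (WBC, albumin, alkaline phosphatase, total bilirubin, calcium, magnesium) rely on the separate Grade 3/4 listing. The status of glucose is unclear: it is not on the graded list, yet 11.1.7.4 uses hyperglycemia as its grading example.

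**The case against.** The strongest objection is reach. The rule acts only on repeats within one visit, and summaries are by scheduled visit. Coagulation is scheduled at screening and afterwards only as clinically indicated (Table 1 in both documents). Baseline is the last value before first dose (SAP 8.1.1), not the most severe. All results are listed, and protocol 9.5.3 says out-of-range values will be identified, which includes INR and PTT. All of this stands and keeps the point minor. It does not make the stated direction right.

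A reader might go further in four ways that the documents do not support.

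- **Prolonged INR or PTT values are always passed over.** That needs reading A. Under reading B they are kept. Only the all-normal case holds on both.
- **Normal platelets or ALT displace abnormal ones.** That needs reading B, which the parenthesis on the severe direction and the sentence on low values argue against. These harms and the abnormal-value INR and PTT harms need opposite readings and cannot be added together.
- **Magnesium is marked wrongly.** It is unmarked, so only high counts, while sodium, potassium, glucose and calcium go both ways. The protocol's one report of low magnesium (1.6.3.2) concerns mocetinostat, an arm never initiated. Marking it High or Low is a consistency suggestion.
- **Phosphate is not collected.** The CRF and the laboratory loader specification are not available here, and protocol 7.2.3 allows additional tests. What is shown is a mismatch between lists.

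**Conclusion.** Two faults stand as written. First, low is the most severe direction for INR and PTT, so the by-visit summary takes the less prolonged value whenever all repeats are normal, and also when one is prolonged if the rule means the lowest value. Second, the hypophosphatemia shift table has no matching parameter in protocol Table 19, SAP Table 6 or the graded list.

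The size is small: 2 of 26 parameters have the wrong direction, and 1 of 11 shift-table parameters has no listed source. No efficacy analysis is touched. How often INR or PTT is repeated within a visit cannot be known from the documents. INR and PTT have no graded safeguard, and the maximum-grade shift should not be taken to protect every graded parameter, since it covers 10 of 16. The conclusion assumes that Table 6 lists INR and PTT under hematology as it appears to; 8.4.6, which names no coagulation category, agrees with that.

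**What to change.** Needed:
- Add a High mark to the Table 6 legend and to the exception wording in 11.1.7.4.1, and apply it to INR and PTT.
- Check the CRF and the laboratory specification for phosphate. If it is captured, add it to Table 6 with the Low mark and to the CTCAE-graded list. If it is not, delete the hypophosphatemia shift table.

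Optional tidying:
- Mark magnesium High or Low, in line with the other electrolytes.
- Reword the selection bullets. One-directional parameters take the value furthest beyond the limit in the severe direction; two-directional parameters take the value furthest outside the normal range. The existing nearest-to-limit rule stays for the case where all values are normal.

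The cost is two or three table marks, one legend line, a few reworded phrases and one decision on phosphate. SAP 4.0 foresees a final version before database lock, so the changes can go in there. They require no new patient procedures.
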